Theory predicts that the impact of the video on subjective life expectancy (and human capital investment behaviors) should be greater the lower the person's baseline survival expectations, as the informational intervention is stronger relative to the person's baseline beliefs. Additionally, theory predicts that the impact of the video on subjective life expectancy (and human capital investment behaviors as well as HIV testing) should be greater the higher a person's baseline perceived lifetime risk of HIV acquisition, as information on the life-prolonging benefits of ART will be irrelevant to someone who believes that they are unlikely ever to contract HIV.

Therefore, we will test the null hypotheses that subjective life expectancy and perceived lifetime HIV risk are not linear effect modifiers of the primary outcomes: change in subjective life expectancy, HIV testing (with the voucher or home-based testing), participation in the training workshop, savings, and the pooled behavioral outcome described above.

The benefits of HIV testing vary with prior knowledge of status. Individuals who are certain that they are HIV-infected and individuals who are certain that they are HIV-uninfected have little incentive to test, suggesting an inverse-U relationship.

Therefore, we will assess for effect modification of the impact of the video on HIV testing by current beliefs about HIV infection, comparing effects among respondents with greater uncertainty about HIV status vs. those with greater stated certainty.

Finally, we will assess for linear effect modification by age (the information may be more impactful on younger participants who have yet to establish behavioral patterns) and sex (a common effect modifier in HIV interventions).

A5. Overview of Study Design

We will conduct a pilot intervention study to learn whether a short video providing young adults with information on recent longevity gains affects survival expectations, hope for the future, and ultimately health and educational behaviors. We intend to recruit approximately 450 young adults ages 18 to 25 for this research project. The study involves the following components:

- Conduct a survey to measure survival expectations and other perceptions of HIV and ART that affect health decision-making as well as health and education (future-oriented) actions,

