Participants were sampled at random from a population listing from AHRI/Africa Centre's surveillance. AHRI's surveillance is organized by geographically defined week blocks. Specific week blocks were chosen for this study based on the timing of AHRI's surveillance. We included respondents residing in week blocks where AHRI was scheduled to conduct its annual surveillance and HIV testing offer about 6-8 weeks after the baseline survey.

Details on the Sampling Strategy are contained in Appendix A.

We chose a target sample size of 450 individuals. The final actual sample size will be determined based on the number of successful interviews achieved within a pre-specified period, from a pre-specified roster of eligible participants. The number of eligible participants included in the study roster is based our target of 450 baseline interviews conducted. Based on prior studies of this age group at AHRI, we anticipate that we will be able to find and recruit 50- 60% of the eligible population. We anticipate that our study team is capable of conducting 60-75 interviews per week. We therefore sampled 120 individuals in each of seven week-blocks for a total of 840 individuals eligible for recruitment. The final sample size was the number of respondents successfully interviewed from the pre-specified study rosters.

With a target sample of 450 individuals, this study is powered at 80% to detect a 0.26 standard deviation difference in outcomes between the treatment and pooled control groups.

Example 1) We are powered to detect an increase in subjective (perceived) life expectancy from 50 to 54 years, assuming a standard deviation of 15 years. The baseline numbers – 50, $sd=15$ – are based on survey pre-tests conducted as part of a prior study: "Life plans of young adults in rural KZN: a qualitative study". A four-year increase would be about a quarter of the actual change in life expectancy that occurred between 2003 and 2014.

Example 2) We are powered to detect an increase in the proportion using the HIV testing voucher (or taking up the job search skills workshop) from 10% to 20%. As this is a pilot study, we are only powered to detect intervention effects if they are large.

A8. Interventions and Randomization

A8.1. Study Arms

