If I were HIV infected, I would want to start ARVs (HIV treatment) as soon as possible, even if I didn't feel sick	
If I were HIV infected, I would prefer to wait as long as possible to start ARVs	X
If I were HIV infected, I would choose not to start ARVs.	X

B1.2 Secondary Outcome Measures

Behaviors

Attendance at job search skills workshop

Definition: Participants will be invited to a job search skills workshop; workshops were held in nearby locations 1-3 weeks after each survey week-block; attendance will be measured as a binary indicator

[Time Frame: 2 weeks]

Condoms purchased

Definition: Participants will be offered the opportunity to purchase discount condoms; the number purchased will be assessed; range 0 to 10 condoms
[Time Frame: Baseline survey]

Savings allocated

Definition: Participants will be offered the opportunity to allocate a portion of their participation incentive to a savings device (lock box); amount allocated will be assessed; range 0 to 100 Rand
[Time Frame: Baseline survey]

Savings at 2-month follow-up

Definition: At follow-up, participants are asked if they still have the savings tin and if they have added money to the tin since baseline. They are then asked to estimate the total savings inside today or on the date when they opened it. If they still have the tin on hand, we then open it, count their savings, and provide them with a new tin to continue saving. We will define 2-month savings in two ways: first, as the amount the participants self-report they have in the tin on the follow-up interview date or, if they no longer have the tin, on the last day they had it; and second, as the amount we validate by opening the tin, with zeroes imputed if the tin is not available or money used.

[Time Frame: 2-months]

Use of HIV testing voucher

Definition: Participants will be provided with a voucher for free HIV testing at a local service provider (we partnered with two local pharmacies that provided government certified HIV testing services); use of voucher will be assessed by obtaining voucher numbers from the service provider

[Time Frame: 1 month]

Uptake of HIV testing in the AHRI surveillance

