Our primary analyses will assess: *intervention video (arm 1, 50%) versus no intervention video (arms 2 and 3, 50%)*. This is the highest powered test we have. It is justified under the *a priori* assumption that the attention placebo control video has no effect on outcomes. Indeed, this is the same assumption that is made (implicitly) any time a placebo control is used, with the assumption justified by the design of the placebo as not having any theoretically active components. We note that this primary analysis rests on an *a priori* assumption. We are not powered to test the null hypothesis that Arms 2 and 3 are the same. And because of limited power, failure to reject the null hypothesis that arms 2 and 3 are the same would not be strong evidence that the null hypothesis is true. Hence, approach 1 is identified under an *a priori* assumption of no difference between arms 2 and 3.

In secondary analyses, we will loosen the a priori assumption and now compare:
A. intervention video (arm 1, 50%) versus attention placebo control (arm 2, 25%)
This comparison assesses the impact of information on survival gains due to ART on outcomes, holding constant the nature of the video intervention (attention control). Therefore, it comes closest to capturing the theoretical construct of interest.

B. intervention video (arm 1, 50%) versus pure control no video (arm 3, 25%)
This comparison assesses the impact of the informational video vis-à-vis standard of care, which is no video. This comes closest to capturing the effect of policy interest. Additionally, this comparison insures us against the possibility that our a priori assumption is incorrect (i.e the placebo video does affect outcomes), giving us an estimate of effect that does not include the effect of the placebo.

B3. Assessment of Balance

We conducted constrained randomization to ensure balance among individuals who were sampled and eligible to participate in the study. However, balance on these factors – as well as other factors not considered in the randomization – is unknown among the participants who are actually recruited into the study.

We will assess balance on the following characteristics that were included in the randomization: sex, age, whether the person was in school, orphan status, HIV positive status, HIV negative status (unknown is the third category), and household asset quintile.

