We will additionally assess balance on all primary and secondary outcomes described above that are measured at baseline.

Through linkage to the AHRI surveillance, we will additionally assess balance on: whether the person has a child; household size; distance to the nearest clinic, whether anyone in the household died from HIV in the prior 10 years; whether anyone in the household is receiving public sector ART at time of baseline.

For each baseline covariate, we will report a t-test for the null hypothesis of equal means in Arm 1 vs. Arms 2+3 (pooled).

B4. Statistical analysis of treatment effects

All statistical analyses will involve comparisons across the treatment arms described above. For each outcome, we will generate the following data:

Example Results Table (fake data)

	Sample Means				Treatment Effect Estimate (95% CI)		
	Arm 1, n=XXX	Arms 2+3, n=XXX	Arm 2, n=xxx	Arm 3, n=xxx	Crude difference	Adjusted for design variables ^a	Adjusted for design, strong predictors, and baseline imbalance ^b
Outcome 1	1.2	1.5			-0.3 (-0.5 to 0.2)	-0.3 (-0.5 to 0.2)	-0.3 (-0.5 to 0.2)
			1.7		-0.5 (-0.8 to 0.0)*	-0.5 (-0.7 to 0.0)*	-0.5 (-0.7 to 0.0)*
				1.4	-0.3 (-0.5 to 0.3)	-0.3 (-0.5 to 0.2)	-0.3 (-0.5 to 0.2)
Outcome 2							
...							
Outcome k							

^aDesign variables are those variables on which balance was explicitly assessed during randomization. ^bStrong predictors of the outcome are those factors in the baseline balance table that are adjusted differences include regression adjustment for stratifying variables, variables used in the constrained randomization, and variables that were not balanced at baseline despite randomization (p-value <0.1 in F-test).

Sample means will be reported for Arm 1, the combined control (Arms 2+3), and for Arm 2 and 3 separately. When assessing changes from baseline to follow-up, we will simply define the outcomes as within-subject “differences” to facilitate comparisons with other outcomes observed only after the intervention.

Crude comparisons of outcomes between treated and comparison arms will be assessed in linear regression models, regressing the outcome on an indicator for treatment arm and indicators for week-block, a stratification variable. We will adjust our standard errors for clustering at the household level, given that error terms without households may be correlated.

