Adjusted effect estimates. We will estimate adjusted effect estimates in multivariate linear regression models. Adjustment for covariates in an RCT has three aims[23]:

- (design variables) to obtain appropriate standard errors when conducting stratified or constrained randomization;
- (strong predictors of the outcome) to reduce residual variance in the outcome, leading to smaller standard errors and narrower confidence intervals; and
- (factors with strong baseline imbalance) to eliminate the impact of any imbalances on observed baseline factors, despite randomization

(a) In our adjusted analyses, we will include the following design variables:

- Stratification variables: week block
- Constrained randomization variables: sex, age, whether the person was in school, orphan status, HIV positive status, HIV negative status (unknown is the third category), and household asset quintile

(b) We will include the following variables believed *a priori* to be strong predictors of HIV testing and human capital investment:

- Distance to nearest clinic
- Baseline subjective life expectancy
- Baseline beliefs about lifetime HIV infection risk

(c) Finally, to eliminate imbalances on observables, we will adjust for variables with $p < 0.1$ for the t-test of differences between Arm 1 and Arm 2+3.

B5. Subgroup analyses

The informational intervention is expected to have the greatest impact for individuals with low baseline survival beliefs and for individuals with high baseline beliefs about lifetime chances of contracting HIV.

Perceived likelihood of lifetime HIV infection. The impact of the informational video is likely to vary by baseline perceived risk of lifetime HIV infection. We will assess for linear effect modification of our primary outcomes by perceived lifetime infection risk.

Baseline survival expectations. The impact of the informational video is likely to vary by baseline survival expectations, with the greatest potential shift in beliefs for individuals with previously low survival expectations. We will assess for linear effect modification of our primary outcomes by baseline subjective life expectancy.

Finally, we will assess effect modification by age (continuous, 18-25) and sex of the respondent (M/F).

B6. Robustness checks

We will subject our primary results (Arm 1 vs. Arms 2+3 for primary outcomes) to robustness checks.

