Logistic regression model. We will also estimate our primary models using multivariate logistic regression to assess sensitivity to specification. In lieu of odds ratios, we will report marginal effects associated with the treatment arm, to enable comparison with the estimate from the OLS models. Again, standard errors will be clustered at the household level.

Restrict to HIV-uninfected. HIV testing uptake – one of our primary outcomes – is less relevant for individuals who already know their current HIV status. In a robustness check, we will assess HIV uptake after excluding: individuals who reported that they had ever tested for HIV and were certain that they were HIV positive at baseline (20 out of 20 beans); and individuals who reported testing for

HIV in the prior 3 months and reported that they were sure that they were HIV negative (0 out of 20 beans).

Remove participants with inconsistent answers and extreme outliers. A small number of participants reported inconsistent answers to the survival expectations questions at baseline. We will assess robustness of results after removing: participants who reported non-zero chances of survival at ages greater than the “oldest possible age” they could imagine living to; participants who reported that it was unlikely they would live to 60 years but allocated >10 beans; participants who reported that it was likely they would live to 60 years but allocated <10 beans. Demographic differences between persons with consistent and inconsistent answers will be reported.

B7. Adjusting Inference for Multiple Hypothesis Testing

No adjustments will be made for our primary outcomes.

For secondary outcomes, the primary manner in which we adjust for multiple hypotheses being tested is by grouping outcomes into indices such that their joint significance will be tested. If we do not find that there is overall significance for aggregated measures of behaviors such as local of control, we will not move test statistical significance of individual index components. In addition, for families of outcomes where we are interested in testing the treatment effect both for an index overall as well as individual components, when the number of tests is large (greater than 10), we adjust our standard errors using the Benjamini-Hochberg procedure[24] for controlling the false discovery rate to less than 0.05.

B7. Handling attrition

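### The predictor list for the fully adjusted HIV-testing estimate omits certainty about current HIV status and prior testing, both collected at baseline, and so gives up some precision

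*Combined protocol and SAP*

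**What the plan says.** The relevant text is spread over several sections of the combined document.

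- **B4, adjusted effect estimates.** Covariates enter for three reasons, one of which is to cut residual variance and so narrow confidence intervals. Item (b) serves that aim. It names distance to the nearest clinic, baseline subjective life expectancy and the belief about lifetime HIV risk as variables thought in advance "to be strong predictors of HIV testing and human capital investment". Item (a) adds week block and the constrained-randomization variables, including surveillance HIV status (positive, negative, unknown). Item (c) adds any variable that differs between Arm 1 and Arms 2+3 at p<0.1.
- **B4, example results table.** Each comparison gets a crude, a design-adjusted and a fully adjusted estimate. Item (b) acts only on the last. The text does not say which of the three is primary. Footnote b, which is garbled, appears to take strong predictors from the baseline balance table rather than from the item (b) list.
- **A4, subgroup analyses.** "The benefits of HIV testing vary with prior knowledge of status". The section goes on to say that people sure of either status have little reason to test, expects an inverse-U, and plans effect modification of the testing effect by uncertainty about status.
- **B6, restriction to HIV-uninfected.** One robustness check drops "individuals who reported that they had ever tested for HIV and were certain that they were HIV positive at baseline", and also those who tested in the prior 3 months and were sure they were negative. Certainty is read from a 0 to 20 bean scale.

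**The concern.** The plan sets out to adjust for strong predictors of testing, explains elsewhere why certainty about one's status should affect testing, and collects that certainty together with testing history. It then leaves both out of the list whose purpose is precision.

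The other provisions do not do the same job:

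- Serostatus in item (a) is what the surveillance holds. It is not what the participant believes or how recently the participant tested.
- Item (c) selects on chance imbalance, which is unrelated to prognostic strength. Recent testing reaches the balance set only inside a combined measure with ARV use (B1.2, B3), and the current-status beans are not listed there.
- The B6 check removes participants and changes the population. It does not reduce residual variance in the full sample.
- The lifetime-risk term is a different belief and enters linearly.
- HIV testing and the composite have no baseline value of their own to adjust for.

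At stake is the width of the fully adjusted confidence interval for HIV testing and, to a lesser degree, for the composite. A7 itself says that the pilot can detect only large effects.

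**Working it through.** **1. Inputs.** From A7: "With a target sample of 450 individuals, this study is powered at 80% to detect a 0.26 standard deviation difference". From B2: half the sample in Arm 1 and half in Arms 2+3, so about 225 per group. Alpha is not stated; two-sided 0.05 is assumed from the 95% intervals in the B4 table. No design effect or dropout is applied.

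**2. The plan's own figure.** Minimum detectable effect (MDE) = (1.960 + 0.842) × √(2/225) = 2.802 × 0.0943 = 0.264 SD, which rounds to the stated 0.26. Power at exactly 0.26 SD is 78.7%. The figure reproduces with no covariate adjustment, so it does not depend on item (b).

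**3. Effect of adding the covariates.** Let R² be the partial R² of the added variables, given those already in the model. The standard error is multiplied by √(1 − R²), and the equivalent sample size is 450/(1 − R²). The documents give no value, so a range of 0.01 to 0.15 is assumed for HIV testing.

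| Partial R² (assumed) | CI width × | MDE (SD) | Power at 0.26 SD | Equivalent N |
|---|---|---|---|---|
| 0 | 1 | 0.264 | 78.7% | 450 |
| 0.01 | 0.995 | 0.263 | 79.2% | 455 |
| 0.05 | 0.975 | 0.257 | 80.8% | 474 |
| 0.10 | 0.949 | 0.251 | 82.8% | 500 |
| 0.15 | 0.922 | 0.244 | 84.9% | 529 |

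**4. What uptake patterns imply.** Suppose a share q knows its status and tests at rate pₗ, while the rest test at pₕ, with mean p. Then R² = q(1 − q)(pₕ − pₗ)²/[p(1 − p)]. All inputs here are assumptions.

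- q = 0.2, 10% vs 40%: p = 0.34; R² = 0.16 × 0.09/(0.34 × 0.66) = 0.064; CI × 0.967.
- q = 0.3, 10% vs 40%: p = 0.31; R² = 0.21 × 0.09/(0.31 × 0.69) = 0.088; CI × 0.955.
- q = 0.4, 5% vs 15%: p = 0.11; R² = 0.24 × 0.01/(0.11 × 0.89) = 0.025; CI × 0.988.

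These are marginal R² values. The partial values would probably be lower, because serostatus and other correlates are already in the model.

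**5. Composite (count 0 to 3).** Suppose the three components have equal variance and are uncorrelated, and the new covariates predict only testing. The composite R² is then one third of the testing R². Testing R² of 0.05, 0.10 and 0.15 gives 0.017, 0.033 and 0.050, and CI width × 0.992, 0.983 and 0.975.

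**6. Coding.** With beliefs spread evenly over 0 to 20 beans, a linear term has zero correlation with a symmetric inverse-U, (beans − 10)². A linear bean count would therefore miss the shape that A4 predicts. The smaller of beans and 20 − beans is 0 at either certainty and 10 at greatest uncertainty, so it can carry that shape.

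**The case against.** The strongest reply is that choosing three prespecified covariates is legitimate, that nothing in the plan is biased or contradictory on this account, and that the gain is unproven and may be small. Much of this stands:

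- The size rests on assumed values. A7 gives only a 10% to 20% planning figure for voucher use or workshop uptake, and no home-test rate. The home-test definition in B1.2 scores everyone not at home as 0, so some outcome variance reflects absence rather than incentive to test.
- Part of any signal is already captured by serostatus and the lifetime-risk belief.
- The plan's support is direct only for certainty. For prior testing it is indirect, through knowledge of status.
- A4's effect-modification analysis would normally include a main effect of certainty, and B6 looks at those who do not already know their status.

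None of this answers the point itself. The A4 analysis is a subgroup question that B5 does not repeat, and the B6 check changes the population. Neither puts these variables in the full-sample model whose declared aim is a narrower interval. That the gain is uncertain argues for modest claims about it. It is not a reason to leave the variables out when the data are in hand.

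**Conclusion.** The omission is real and worth correcting as an efficiency matter. It affects the fully adjusted estimate for HIV testing and its voucher and home-test components, with a smaller effect on the composite. The numerical ranges depend on the assumed R² and, for the composite, on equal-variance, uncorrelated components.

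Three stronger readings are tempting, and the documents do not support them:

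- **That both behavioural primary results are made less precise across the board.** The crude and design-adjusted estimates do not use item (b), and the plan does not name the fully adjusted column as the primary result. The composite gains only about a third as much in R².
- **That the power statement is wrong.** It reproduces without any adjustment.
- **That clinic distance should give way to pharmacy distance**, because for the voucher "we partnered with two local pharmacies that provided government certified HIV testing services". B3 obtains clinic distance through AHRI linkage, but nothing shows that pharmacy distance can be derived in the same way. It would also bear only on the voucher route, since the other route is a home visit. No change to the distance covariate is proposed.

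**What to change.** Amend B4(b) before unblinding. For the fully adjusted estimates of HIV testing, voucher use, home-test uptake and the composite, add:

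1. certainty of current HIV status, coded as the smaller of beans and 20 − beans;
2. tested for HIV in the prior 3 months (yes/no);
3. ever tested (yes/no).

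Specify that these are pre-video answers, and confirm from the questionnaire that they fall in the A9.1 module. In the same edit, make B4(b) and footnote b of the results table give one definition of strong predictors.

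The cost is SAP wording and about three degrees of freedom out of about 450, with no new data collection. A12 schedules unblinding for the day after the plan is posted. If unblinding has already happened, report this adjustment as a supplementary analysis and label it as added afterwards.
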